
Primary Objectives

We will study the effectiveness of highly innovative transplant social worker led interventions that intervene on key knowledge, interpersonal, logistical and financial barriers to live kidney donation for African Americans patients on the deceased donor kidney waiting list.

Objectives and Hypothesis

- A. Transplant Social Worker Educational and Behavioral Intervention.** In our previous work, we developed the Talking About Live Kidney Donation Social Worker Intervention (TALK SWI), a culturally sensitive educational and behavioral intervention to improve consideration and pursuit of live donor kidney transplants among patients with chronic kidney disease (CKD) and their families. TALK SWI is tailored to accommodate patients with low reading (i.e., 4th grade) and health literacy levels and helps patients and their

families overcome self-identified interpersonal barriers to discussing and pursuing live donor kidney transplants. TALK SWI educational materials were determined to be culturally sensitive based on our conduct of 8 focus groups of African American and non-African American patients with chronic kidney disease (with and without live donor kidney transplant experience) and their family members identifying their concerns about live donor kidney transplantation¹⁹. In a recently completed randomized controlled trial, we found TALK SWI was effective in improving rates of consideration and pursuit of pre-emptive live donor kidney transplantation among patients with stage 4 CKD not yet on dialysis.²² We propose to study the effectiveness of the TALK SWI intervention to activate live kidney donation among African Americans who have recently registered on the transplant waiting list. We hypothesize the TALK SWI will be a powerful catalyst to increase live kidney donation for these patients who have already overcome some barriers to live donor kidney transplantation (i.e., completed the transplant evaluation).

B. **Transplant Social Worker Financial Assistance Intervention.** We hypothesize a financial assistance intervention delivered by transplant social workers to help patients and their potential donors overcome logistical and financial obstacles to live donor kidney transplantation will be well-received by social workers, patients, and their families.

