A. Study population: We will recruit a total of **300 (100 per each study arm) adult African American patients with ESRD who are currently on the deceased donor kidney waiting list with no prior kidney transplant** from the Duke Kidney and Pancreas Transplant Program (DKPTP). The DKPTP cares for a highly diverse set of patients with ESRD, with nearly 55% of the deceased donor kidney transplant waiting list comprised of African Americans annually. As of January 2014, the DKPTP had 297 (55%) African American patients registered on the deceased donor kidney waiting list. DKPTP added approximately 100 new African American waiting list registrants per year in 2012 and 2013. African Americans on the deceased donor kidney waiting list at DKPTP are sociodemographically diverse, and reflect the local Durham, NC population in which 19% have incomes below the Federal Poverty Level. **50**

B. Study Setting: The kidney/pancreas transplant program at DKPTP is a highly innovative center, providing national leadership in the development and implementation of numerous clinical strategies to improve rates of live kidney donation and donor safety (performed first kidney transplant in NC and had performed their 3000th kidney transplant in 2010). The center also features a complete team of transplant surgeons, nurse transplant coordinators, administrative transplant coordinators, psychologists, and social workers to support both potential recipients' and donors' medical and psychosocial needs. The program currently does not have a social worker program tailored specifically to address knowledge, interpersonal, logistical or financial barriers to LDKT in African American potential recipients.

C. Study Design: We will recruit, enroll and then randomly assign participants to one of three study conditions ("arms"). We will follow participants actively for 1 year to assess the effectiveness of interventions to improve live kidney donation and receipt of LDKT among study participants.

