3.1 Primary and Secondary Outcomes

1. Live kidney donor activation (primary): per the protocol, “defined as the composite rate of live kidney donor inquiries on behalf of patient participants, completed live kidney donor transplant evaluations, and live kidney donor transplants in each arm, ascertained via medical records maintained by the Duke Kidney and Pancreas Transplant Program.”

In other words: For each participant, the total number of donor inquiries, evaluations, and LDKT over a 12-month period will be summed and defined as the live donor activation score. For example, if a participant had 5 inquiries, 2 evaluations, and an LDKT, then this person’s score would be 8.

In sensitivity analyses, we will look at these individually, and the composite at 24 months.

2. Pursuit of LDKT (secondary) (scenario): Assessed by two questions, Q1: “Has a family member or friend told you that they would give you a kidney?” And Q2: “Have you talked with family and/or friends about the possibility of someone giving you a kidney?”. Participants will be categorized into 3 groups: 3=identified a donor (answered “yes” to Q1); 2=talked with family members/friends but did not identify a donor (“no” to Q1 and “yes” to Q2); 1=did not talk to family members/friends (“no” to Q1 and Q2). Note that once a person has reached a level, he cannot regress to a previous level, e.g., if at level 2 at randomization, the person cannot be at level 1 at month 4.

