4.1.1 Poisson / ZIP Regression

Note that this section is no longer the main approach and is omitted from the final manuscript.

4.1.1.1 12-month composite activation

The live kidney donor activation score will be compared across study groups using an ANOVA or Kruskal-Wallis test as appropriate. We will then use Poisson regression to determine if the mean rate of activation over 12 months differs by intervention arms. Specifically, we will fit a model of the form

$$g(\mu) = \beta_0 + \beta_1(\text{Arm2}) + \beta_2(\text{Arm3}).$$

Arm2 and Arm3 are indicators of study arm. A Vuong test for comparing non-nested models will be used to test the null that the Poisson and zero-inflated Poisson (ZIP) models are equally close to the true model. If the test rejects in favor of the alternative that the ZIP model is closer, a ZIP will be presented.

In ZIP models, individuals are separated into two groups: those not at risk of an activation (i.e. the excess zeros) with probability ψ , and those who are with probability $1 - \psi$. Then, among those at risk, the activation counts are assumed to be generated from a Poisson process with mean μ . The overall (marginal) distribution of activation score is then

$$Y = \begin{cases} 0 & \text{with probability } \psi \text{ if not at risk} \\ e^{-\mu} \mu^y / y! & \text{with probability } 1 - \psi \text{ if at risk} \end{cases}$$

And the marginal probability function for $P(Y = y)$ is

$$P(Y = 0) = \psi + (1 - \psi)e^{-\mu}$$

$$P(Y = y) = \frac{\psi e^{-\mu} \mu^y}{y!}, \quad y > 0.$$

Denote the prevalence of activation as $\pi = P(Y > 0) = 1 - P(Y = 0) = (1 - \psi)(1 - e^{-\mu})$. Note that the overall mean activation count is $\nu = E(Y) = \mu(1 - \psi)$, and $\text{Var}(Y) = E(Y)(1 + \psi\mu)$, which shows that the variance exceeds the mean when $\psi > 0$. Of primary interest is comparison of the prevalence (π) and overall mean (ν) activation.

The parameter ψ will be modeled by the following logit:

$$\text{logit}(\psi) = \gamma_0 + \gamma_1(\text{Arm2}) + \gamma_2(\text{Arm3}) + \gamma_3(\text{blACT}).$$

blACT is the activation score at randomization (inquiries + evaluations before randomization).

The corresponding Poisson part will be modeled as

$$\log(\mu) = \beta_0 + \beta_1(\text{Arm2}) + \beta_2(\text{Arm3}) + \beta_3(\text{blACT})$$

This models the mean activation counts among those at risk using log-linear models.

4.1.1.2 12-month donor inquiry alone

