$$\lambda_k(t) = \lim_{\Delta t \rightarrow 0} \frac{P(t \leq T < t + \Delta t, K = k | T \geq t)}{\Delta t}$$

This is the instantaneous *rate of event k* at time t , in subjects *who have experienced none of the events* (of any type) before time t .

Both subdistribution and cause-specific hazard models will be fit, having the form

$$\lambda_k(t) = \log\{\lambda_{k0}(t)\} + \beta_1(\text{arm2}) + \beta_2(\text{arm3}).$$

Here, $\lambda_{k0}(t)$ denotes the hazard function for participants in arm 1, and “arm2” and “arm3” are indicator variables. Interest lies in β_1 and β_2 , the increased hazard of each event being in the intervention arms compared to the control arm.

4.1.2.2 12-month donor inquiry alone

A similar survival approach described above will be used to model time to first inquiry (ignoring evaluations and LDKTs) in the presence of the competing risks DDKT and death.

4.1.2.3 12-month donor evaluation alone

A similar survival approach described above will be used to model time to first evaluation (ignoring inquiries and LDKTs) in the presence of the competing risks DDKT and death.

4.1.2.4 12-month LDKT

Though it is likely not possible or even meaningful with only 4 events, a similar survival approach will be used to model time to LDKT (ignoring inquiries and evaluations) in the presence of the competing risks DDKT and death.

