4.2.1 Continuous Formulation of Scenario

We will model scenario as a continuous variable and use longitudinal GEEs (normal outcome) with an unstructured correlation matrix to determine if the total scenario changes over time for each arm. Specifically, we will fit a model of the form

$$\begin{aligned} g(\mu) = & \beta_0 + \beta_1(\text{Arm2}) + \beta_2(\text{Arm3}) + \beta_3(4\text{mo}) + \beta_4(12\text{mo}) \\ & + \beta_5(\text{Arm2} \times 4\text{mo}) \\ & + \beta_6(\text{Arm3} \times 4\text{mo}) + \beta_7(\text{Arm2} \times 12\text{mo}) + \beta_8(\text{Arm3} \times 12\text{mo}). \end{aligned}$$

Because all the variables are indicator functions, the right hand side reduces to

	Arm 1	Arm 2	Arm 3
Baseline	β_0	$\beta_0 + \beta_1$	$\beta_0 + \beta_2$
4 months	$\beta_0 +$ β_3	$\beta_0 + \beta_1 + \beta_3 +$ β_5	$\beta_0 + \beta_2 + \beta_3 +$ β_6
12 months	$\beta_0 +$ β_4	$\beta_0 + \beta_1 + \beta_4 +$ β_7	$\beta_0 + \beta_2 + \beta_4 +$ β_8

We will assess the changes in scenario within each arm, and then determine if there is a difference across arms at 12 months. Note that the difference from baseline to 12 months within each arm is given by

	Arm 1	Arm 2	Arm 3
4 months - Baseline	β_3	$\beta_3 + \beta_5$	$\beta_3 + \beta_6$
12 months - Baseline	β_4	$\beta_4 + \beta_7$	$\beta_4 + \beta_8$

If β_7 is non-zero, the change from baseline in Arm 2 is significantly different than the change from baseline in Arm 1. Similarly, if β_8 is non-zero, the change from baseline in Arm 3 is significantly different than the change from baseline in Arm 1.

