4.2.3 Number of Steps Forward

The number of steps the participant moved forward at each follow-up visit will also be modeled with a GEE. Of interest is the number of steps moved from baseline to month 4, and from month 4 to month 12. All participants had baseline data. If participant was missing a M4 or M12 value, then 0 steps taken was imputed as the most conservative estimate. If participant was missing a value due to receipt of transplant, then the person was dropped from the analyses at the time of transplant reporting and thereafter.

Participants are not able to go back in scenario, thus if M4 scenario is less than baseline, or if M12 scenario is less than M4 (or baseline) then 0 steps will be imputed.

We will also fit a linear model looking at the total number of steps across the whole study, and a logistic regression model looking at any steps forward across the whole study as an outcome.

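### The primary hazard models leave out a baseline activation score that the SAP already defines, and the steps-forward models name no baseline level: the tests are valid, but power or precision may be lost

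*SAP*

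**What the plan says.** SAP 4.1.2 is marked as the primary approach. For time to first activation event it states "Both subdistribution and cause-specific hazard models will be fit, having the form" of a log baseline hazard plus terms for arm 2 and arm 3. The baseline hazard is that of arm 1 participants, so no further covariate is implied. Sections 4.1.2.2 to 4.1.2.4 use a similar approach for inquiry, evaluation and LDKT alone.

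The SAP defines a baseline covariate in 4.1.1.1: blACT "is the activation score at randomization (inquiries + evaluations before randomization"). It enters both parts of the zero-inflated Poisson (ZIP) model and appears nowhere else. That section is marked as no longer the main approach and as left out of the manuscript.

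For the secondary scenario outcome (levels 1 to 3), SAP 3.1 says "Note that once a person has reached a level, he cannot regress to a previous level". Section 4.2.3 plans a GEE for steps at each visit, then says "We will also fit a linear model looking at the total number of steps across the whole study", and adds a logistic model for any step. None of the three is written out and no baseline level is named, although "All participants had baseline data". A missing month-4 or month-12 value is counted as 0 steps, except after a transplant.

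**The concern.** Prior inquiries and evaluations could well predict later ones. If they do, an arm-only hazard model averages over patients with different underlying rates. The hazard ratio (HR) is pulled towards 1 and power falls. The authors planned to use blACT in one model, and the SAP does not say why it is absent from the approach that replaced it.

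In 4.2.3 the link holds by construction. With no regression allowed, the maximum number of steps is 3 minus the baseline level: 2, 1 or 0. Leaving level out puts variation that is known at baseline into the residual.

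The stake is efficiency in a trial of 100 per arm for which neither document states a power calculation. Type I error and bias are not at stake.

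**Working it through.** **No figure to reproduce.** The documents give 300 patients, 100 per arm, and 12 months of follow-up. They give no alpha, target effect, activation rate, blACT distribution, prognostic strength, baseline scenario mix or transition probabilities. All of these are assumed below, with two-sided alpha 0.05.

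**Hazard models, composite.** Cox simulation with 2,000 three-arm trials per setting. Both active arms have conditional HR 1.8, and the competing hazard is -ln(0.88) per year. blACT is 0, or 1 + Poisson(0.8) if positive, and is fitted as a linear count. The ranges cover control activation of 25% and 35%, both hazard models, and a true effect that is either yes/no or log-linear in the count.

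| Share with prior activity / its HR | Power gain (points) |
|---|---|
| 20% / 1.5 | 0.0 to 1.1 |
| 30% / 2 | 0.9 to 4.2 |
| 40% / 3 | 2.9 to 13.1 |
| 40% / 4 | 4.1 to 17.9 |

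A check at 30% control activation gave 64.2% to 65.5% (30%/HR 2) and 59.3% to 63.3% (40%/HR 3). A simulation built differently (HR 1.75, control 30%, negative binomial blACT with mean 1) gave these changes in cause-specific power:

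- HR 1.0 per blACT unit: 65.5% to 65.5%
- HR 1.25: 61.4% to 63.4%
- HR 1.5: 56.6% to 64.6%
- HR 2.0: 41.7% to 61.5%

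The gain does not come from a smaller standard error (SE). In the first simulation the SE of the log HR rises by 0.3 to 1.0%, while the cause-specific HR moves from 1.61-1.81 unadjusted to 1.77-1.83 adjusted. With no arm effect, rejection is 4.1 to 5.3% unadjusted and 4.2 to 5.9% adjusted.

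**Sparse components.** At control rates of 5 to 10% the change in power is -0.5 to +0.9 points from a base of 12 to 29%, even at 40%/HR 3. That is within or near simulation error.

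**Linear total steps, by hand.** Assume 30/40/30% at levels 1/2/3. In control, level 1 moves +1 with probability 0.30 and +2 with 0.10, and level 2 moves +1 with 0.20. In the treated arms these are 0.40, 0.15 and 0.30.

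- Control, total variance: 0.3×0.70 + 0.4×0.20 − 0.23² = 0.2371. Within level: 0.3×0.45 + 0.4×0.16 = 0.199.
- Treated, total variance: 0.3×1.00 + 0.4×0.30 − 0.33² = 0.3111. Within level: 0.3×0.51 + 0.4×0.21 = 0.237.
- Pooled over one control and two treated arms: total (0.2371 + 2×0.3111)/3 = 0.2864; within (0.199 + 2×0.237)/3 = 0.2243.
- SE ratio: √(0.2243/0.2864) = 0.885, a fall of about 11%, as in simulation.

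Now set a random 20% (assumed) to 0 steps, as 4.2.3 does for missing visits. Means and second moments are multiplied by 0.8.

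- Total variance: 0.1981 (control) and 0.2663 (treated), pooled 0.2436.
- Within level: 0.1738 and 0.2189, pooled 0.2039.
- SE ratio: √(0.2039/0.2436) = 0.915, a fall of about 8%.

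Over 16 assumed settings with complete data, the SE falls 3 to 26% and power rises 1.9 to 16.5 points. With 20% set to 0, an SE reduction of 11% becomes 8% and one of 25% becomes 17%; the power gains become 3.5 and 7.4 points.

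**Steps GEE.** Over 8 settings with complete data, the SE falls 6 to 21% and power rises 3.0 to 11.2 points. Zero imputation was not applied here.

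**Any-step logistic model.** In one assumed setting, adding level raises the SE of the log odds ratio from 0.31 to 0.36, yet power rises from 52% to 64% because the conditional odds ratio is further from 1. Level-3 patients cannot have the event. With categorical level in the model their coefficient diverges, and the arm estimates equal those from levels 1 and 2 alone.

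**The case against.** **No error is shown.** This stands. Arm-only models match the unadjusted tests in 4.1 and the cumulative incidence curves by arm, and adjustment changes the HR from marginal to conditional. A reader might infer that the arm-only results are biased, or that chance imbalance in prior activity would distort them. The documents do not support that: assignment follows the baseline questionnaire, and the confidence intervals already allow for chance imbalance. A reader might also infer a broken commitment. There was none: the plain Poisson model was arm-only too, and the ZIP model depended on a Vuong test.

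**Prior activity may be rare.** The protocol's objectives speak of "African Americans who have recently registered on the transplant waiting list", which points to the low end of the range. Against that, "As of January 2014, the DKPTP had 297 (55%) African American patients registered on the deceased donor kidney waiting list", with about 100 new registrants a year, and eligibility asks only that a patient be on the list. Two years of new registrants is 2×100 = 200, so filling 300 places in that window would take at least 100 from the standing list. Recruitment may run longer, so this makes prior activity plausible but does not size it.

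**blACT may be less ready than it looks.** This stands in part. The statement that everyone had baseline data is made about scenario. SAP 2.1 describes record data up to 12 months after randomisation, and no look-back window is given for blACT.

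**Timing.** This stands. SAP 4.1.2.4 already cites 4 LDKT events, so some outcome counts were known. A covariate added now creates a second candidate primary result.

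**The steps models.** They are supplementary and not written out, so arm-only is a reading of silence. It would be wrong to extend the point to all scenario analyses: the GEE in 4.2.1 carries baseline as a time point ("Note that the difference from baseline to 12 months within each arm is given by"), and 4.2.2 uses a similar GEE. Nor is there a level-3 defect in the plan as written. In an arm-only logistic model those patients simply count as no step; the divergence appears only once level is added.

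**Conclusion.** The point holds as an efficiency suggestion, to be considered rather than required. The primary hazard models omit a covariate that the SAP defines, and 4.2.3 omits one that bounds its outcome.

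For the composite, the gain is near zero if prior activity is rare or weakly predictive and about 1 to 4 points in moderate settings. Gains towards 18 points need 40% prevalence, HR 4 and a log-linear effect. The documents fix none of these inputs. Evaluation alone and LDKT give no support for adjustment if events are sparse.

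The steps limb is firmer, because the cap follows from the scoring rule. Its size still depends on the assumed mix and transitions, and the complete-data figures overstate it once missing visits are set to 0. Confidence is medium.

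**What to change.** - **Primary models.** Add blACT, in the single linear-count form of 4.1.1.1, to the cause-specific and subdistribution models for composite activation and, if events are common enough, for inquiry alone. Leave evaluation alone and LDKT unadjusted. Confirm that blACT is held for all randomised patients and state its look-back period. State that the HR is conditional on blACT.
- **Which result governs.** Date the change, report arm-only results alongside, and name the governing result in advance. If outcomes by arm have been seen, keep arm-only as primary and label the adjusted fit a sensitivity analysis.
- **Section 4.2.3.** Write the models out and add categorical baseline level to the linear and GEE models. If level is also added to the logistic model, fit it in levels 1 and 2, label that population, and note that the gain is in power while the SE rises. Do not adjust for month-4 level, which is measured after randomisation.

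The cost is one covariate per model and, if blACT is held as defined, no new data. The downsides are a conditional HR, an SE of the log HR up to about 1% larger, and possibly no gain on the primary outcome.

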controlled trial to test the effectiveness of these transplant social worker led interventions as *Reinforcing* (through the effect of educational video and booklet providing basic education about LDKT and emphasizing the importance of engaging in discussion and pursuit of LDKT) and *Enabling* (by providing social worker support for family discussions about LDKT and by providing financial support to overcome logistical and financial barriers to live kidney donation). We hypothesize that the behavioral intervention will lead to patients' and families' greater pursuit of LDKT compared to usual care and the financial assistance intervention paired with the behavioral intervention will be most effective in increasing LDKT among African Americans on the kidney waiting list. Our primary outcomes will measure potential live kidney donors' activation toward donating.

Overview of General Approach

We will study the incremental effectiveness of (1) an educational and behavioral social worker intervention and (2) a live donor financial assistance intervention to improve live donor activation and live kidney donation for African American patients on the deceased donor kidney transplant waiting list. The proposed mechanisms through which the interventions intervene on knowledge, interpersonal, financial, and logistical barriers to LDKT are listed in **Table 1**. In a two-phase study, we will first adapt the previously developed Talking About Live Kidney Donation (TALK) Social Worker protocol for use with transplant social workers (Phase 1), and we will then conduct a randomized controlled trial (Phase 2) to study the effectiveness of interventions to improve pursuit of LDKT (in recipients) and live kidney donation (among potential donors).

Study Interventions

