Arm 1. Usual Care (N=100): Participants randomly assigned to this arm will receive their usual care with the transplant team while awaiting a deceased donor kidney transplant. Participants are periodically contacted (approximately once per year) to establish their continued desire to be listed on the waiting list and to address any administrative issues related to transplant (i.e., updated contact and insurance information) by the DKPTP. They will be mailed the booklet and video at the end of the study.

Arm 2. TALK SWI (N=100): Participants randomly assigned to this arm will receive the TALK SWI delivered by a transplant social worker.

Arm 3. TALK SWI Plus Financial Assistance (N=100): Participants randomly assigned to receive the TALK SWI Plus the Financial Assistance for Living Donor Expenses will receive the TALK SWI as described for Arm 2. Study staff will also provide participants with information about the study Live Donor Financial Assistance Intervention, and provide instructions on how to use the Intervention (details on Financial Assistance Intervention described above)

D. Study Outcomes and Assessments: We perform assessments at baseline, 4 months and 12 months for all participants in Arms 1, 2 and 3. Transplant coordinators at DKPTP routinely capture names and contact information of potential donors contacting the center to inquire about donation procedures on potential recipients' behalves and enter it in the Phoenix (PHX) transplant application, which is part of the EpicCare Ambulatory

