Transplant Social Worker Support for Live Kidney Donation in African Americans

Statistical Analysis Plan
Document Date: August 3, 2020

NCT02369354

1 Study Overview

"The Talking about Living Kidney Donation Support (TALKS) study is a randomized controlled trial designed to test the incremental effectiveness of (1) a culturally sensitive educational and behavioral social worker intervention and (2) a live donor financial assistance intervention to improve potential kidney recipient activation (i.e., discussions with physicians and family about live donor kidney transplant [LDKT]) and live kidney donation among African American patients on the deceased donor kidney transplant waiting list at Duke University Medical Center."

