4.2.2 Dichotomous Formulation of Scenario

We will also dichotomize the scenario into maximum activation (talked with family/friends and identified a donor) vs less activation (talked with family/friends but did not identify a donor, or did not talk to family/friends). We will use a similar GEE (binomial outcome) to determine if the probability of having maximum activation over time is different between arms.

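### Both documents state an incremental purpose, but the supplied SAP body interprets effects only against usual care and states no Arm 3 versus Arm 2 contrast

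*SAP*

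**What the plan says.** **Purpose.** The protocol, under Overview of General Approach, says: "We will study the incremental effectiveness of (1) an educational and behavioral social worker intervention and (2) a live donor financial assistance intervention". SAP section 1 describes the trial as "designed to test the incremental effectiveness of (1) a culturally sensitive educational and behavioral social worker intervention", with the donor financial assistance intervention as the second component.

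**Arms.** The protocol's Study Design section says Arm 3 participants "will receive the TALK SWI as described for Arm 2", and in addition are offered the financial assistance.

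**Primary analysis.** SAP 4.1.2.1 fits subdistribution and cause-specific hazard models with indicators for Arms 2 and 3 and Arm 1 as reference. Interest is stated to lie in β1 and β2, described as "the increased hazard of each event being in the intervention arms compared to the control arm". Sections 4.1.2.2 to 4.1.2.4 reuse this approach for each component.

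**Secondary analysis.** SAP 4.2.1 interprets β7 and β8. For β8 the reading is that "the change from baseline in Arm 3 is significantly different than the change from baseline in Arm 1"; β7 is the same for Arm 2 against Arm 1. The section also intends to "determine if there is a difference across arms at 12 months", and 4.2.2 to "determine if the probability of having maximum activation over time is different between arms", neither naming a pair. SAP 4.2.3 lists models such as "a logistic regression model looking at any steps forward across the whole study as an outcome" without stating an arm term.

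**Other framing.** SAP 1.1.1 and 1.2.1 and the protocol's Study Phase 2 text use usual care as the comparator. SAP 1.1.1 refers to a Table 2 in an appendix that is not in the supplied text.

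**The concern.** The three arms are nested. Arm 2 versus Arm 1 estimates the effect of TALK SWI, Arm 3 versus Arm 1 the effect of the package, and only Arm 3 versus Arm 2 the effect of adding financial assistance to TALK SWI. An incremental purpose with two numbered components needs the first and the third. The supplied SAP body interprets the first and the second.

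This matters because the protocol says twice (Objectives and Hypothesis; Live Donor Financial Assistance Intervention) that, if the financial intervention proves effective, it would support widening the existing donor assistance programme. A favourable package effect cannot carry that conclusion alone, since it is compatible with no contribution from the money. The SAP overview and the SAP's own aim also do not match: one is incremental, the other is against usual care.

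**Working it through.** **1. Each between-arm comparison in the supplied SAP body**

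| SAP section | Comparison | Arm 3 vs Arm 2 stated? |
|---|---|---|
| 4.1 | Kruskal-Wallis or Fisher's exact test across arms | No; omnibus |
| 4.1.1 (set aside by the SAP) | Poisson/ZIP, Arm 1 as reference | No |
| 4.1.2.1 to 4.1.2.4 | β1, β2 against Arm 1 | No |
| 4.2 | Crosstab by arm, chi-squared or Fisher | No; omnibus |
| 4.2.1 | β7, β8 against Arm 1; a 12-month difference across arms | No; no pair named |
| 4.2.2 | Difference between arms | No; no pair named |
| 4.2.3 | Steps forward | No arm term stated |

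**2. Why the two usual-care effects do not settle the increment**

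The Arm 3 versus Arm 2 hazard ratio is exp(β2 − β1). Illustrative values:
- hazard ratios of 1.5 and 1.5 against usual care give 1.5/1.5 = 1.00;
- hazard ratios of 1.5 and 2.25 give 2.25/1.5 = 1.50.

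A reader can form this ratio from the reported coefficients, but its interval also needs their covariance, because they share the control arm. With d events in every arm, Var(β2 − β1) = 2/d. Adding the two variances as if independent gives 4/d. At an assumed 30 events per arm, the 95% interval factor is exp(1.96·√(2/30)) = 1.66 with the correct variance and exp(1.96·√(4/30)) = 2.05 without the covariance.

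**3. Precision of the contrast**

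The documents give no power calculation, alpha or composite event rate, so there is no planned figure to reproduce. From the protocol: 100 per arm. Assumed: usual-care 12-month activation p0 of 10–40%; Arms 2 and 3 equal at hazard ratio H of 1.0, 1.5 or 1.8 against usual care; proportional hazards; no loss to competing events. Then:
- events per arm: d = 100·[1 − (1 − p0)^H];
- SE of the log hazard ratio: √(1/d + 1/d);
- interval factor: exp(1.96·SE).

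Example: p0 = 0.4 and H = 1.8 give d = 60.1, SE = √(2/60.1) = 0.182 and factor 1.43.

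| p0 | SE (factor), H = 1.0 | SE (factor), H = 1.5 | SE (factor), H = 1.8 |
|---|---|---|---|
| 10% | 0.447 (2.40) | 0.370 (2.06) | 0.340 (1.95) |
| 20% | 0.316 (1.86) | 0.265 (1.68) | 0.246 (1.62) |
| 30% | 0.258 (1.66) | 0.220 (1.54) | 0.205 (1.50) |
| 40% | 0.224 (1.55) | 0.193 (1.46) | 0.182 (1.43) |

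**4. Power, as a guide to how the contrast should be used**

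At a two-sided 5% level (assumed), with Arm 2 at 1.0–1.8 against usual care, Arm 3 at r times Arm 2 and the same p0 range, power is Φ(ln r/SE − 1.96) plus the negligible opposite tail, with SE = √(1/d2 + 1/d3):
- r = 1.3: about 10–32%;
- r = 1.5: about 17–65%.

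**5. Transplants alone**

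SAP 4.1.2.4 gives 4 LDKT events in total. Even if they fell 2 and 2 in Arms 2 and 3, SE = √(1/2 + 1/2) = 1.0 and the interval factor is exp(1.96) = 7.1.

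**The case against.** The SAP's operative parts agree with each other: aim, primary hypothesis and interpreted coefficients are all against usual care, and the protocol's Phase 2 text uses the same comparator. The incremental sentence in SAP section 1 is a quoted study description. The protocol's own hypothesis for the financial intervention is that it will be well received, and SAP 1.1.2 and 1.2.2 treat use of the programme as descriptive. This stands in part: the usual-care comparison is a legitimate aim. It does not remove the mismatch with the incremental purpose in both documents, nor does it support a policy claim conditional on the financial component being effective.

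The contrast is also easy to derive and will be imprecise. Both are true. Ease of derivation makes the change cheap, and imprecision is a reason to show the interval rather than let readers compare two results against usual care.

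A reader might infer more than the documents support:
- *That the increment is not planned at all.* Table 2 of the appendix was not available, and the wording in 4.2.1 and 4.2.2 that names no pair does not exclude this comparison.
- *That an interval is missing for this contrast in particular.* The SAP body commits to no confidence interval for any contrast, β1 and β2 included.
- *That the contrast would test the additive hypothesis, or the prediction that the combined arm does most to increase LDKT.* Without a finance-only arm it gives the financial effect only on top of TALK SWI, and 4 events cannot usefully test a claim about LDKT.

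**Conclusion.** The point holds for the supplied SAP body. An Arm 3 versus Arm 2 contrast is not stated there, and following the text as written would report TALK SWI and the package, each against usual care, without isolating the financial increment.

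Under the stated assumptions, the log hazard ratio would have an SE of about 0.18–0.45, so a 95% interval of the estimate multiplied or divided by about 1.4–2.4. Power for modest increments is low. The textual finding does not depend on these figures; they show only that the contrast should be read through its interval.

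The usual-care comparisons are not invalid, and the gap can be closed without new data. Severity is minor to should-fix, with medium confidence because the appendix could not be checked.

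**What to change.** 1. In SAP 4.1.2.1, add β2 − β1 for the activation event as the one lead contrast. Report it as the Arm 3 versus Arm 2 hazard ratio with a 95% CI, using the model covariance, in both hazard models. Report 95% CIs for β1 and β2 as well.
2. As supporting estimates without formal testing, add β8 − β7 in 4.2.1 and the matching contrasts in 4.1.2.2 and 4.2.2. Add 4.1.2.3 only if the number of evaluations supports it. Leave out 4.1.2.4 (4 events) and 4.2.3 (no arm term stated).
3. Date the addition. The SAP already cites an event count and a manuscript, so label the contrast as added after data were available, and as post hoc if arm-level results had been seen.
4. If appendix Table 2 already lists the contrast, cite it in 4.1.2.1 and 4.2.1 instead.
5. Only if the sponsor chooses not to report the contrast, restate the objective and the policy claim as TALK SWI plus financial assistance versus usual care.

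Cost: some SAP wording and one linear contrast per listed model. Downsides: an imprecise estimate, several extra contrasts (hence a single lead), and a result that cannot be called prespecified before data were available.
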